1. INTRODUCTION

The purpose of this Statistical Analysis Plan (SAP) is to provide detailed descriptions and methods to be used for efficacy and safety analyses for Protocol 1042-SE-3003. This SAP is based on the Protocol 1042-SE-3003 amendment 5 (06May2024).

The structure and content of this SAP provides sufficient detail to meet the requirements identified by the Food and Drug Administration (FDA) and International Council for Harmonization of Technical Requirements for Registration of Pharmaceuticals for Human Use (ICH): Guidance on Statistical Principles in Clinical Trials.¹ All work planned and reported for this SAP will follow internationally accepted guidelines for statistical practice published by the American Statistical Association.²

This is a double-blind, randomized, placebo-controlled study to evaluate the efficacy and safety of ganaxolone IV solution in status epilepticus (SE), with the option to transition the study to an open-label phase to obtain additional safety data. Unless stated otherwise, the analyses covered in this SAP apply to the double-blind phase of the study. The protocol contains additional details on study design, study conduct, and other operational aspects.

1.1 Study Objectives

1.1.1 Primary Objective

The primary objective of the study is to evaluate the efficacy and safety of intravenous (IV) ganaxolone (GNX) for the treatment of SE after failure of two or more antiseizure medications.

1.1.2 Secondary Objectives

The secondary objectives of the study are the following:

- Assess time to SE cessation following ganaxolone administration.
- Evaluate sustained efficacy of IV ganaxolone beyond the 48-hour treatment period as assessed by prevention of progression to IV anesthesia for the treatment of SE.

1.1.3 Exploratory Objectives

The exploratory objectives of the study are the following:

- Determine the effect of ganaxolone on healthcare resource utilization.
- Assess the effect of ganaxolone on doses of other antiseizure treatments and changes in seizure burden.

- Evaluate the effect of ganaxolone on quality of life, functional status, and level of responsiveness.

1.2 Study Endpoints

1.2.1 Primary Endpoints

The following co-primary endpoints are established to support the primary objective of the study:

- Proportion of participants with SE cessation within 30 minutes of investigational product (IP) initiation without medications for the acute treatment of SE.
- Proportion of participants with no progression to IV anesthesia for 36 hours following IP initiation.

1.2.2 Key Secondary Endpoints

The following key secondary endpoints will be analyzed:

- Time to SE cessation following IP initiation.
- Proportion of participants with no progression to IV anesthesia for 72 hours following IP initiation.

1.2.3 Other Secondary Endpoints

The following additional secondary endpoints will be analyzed:

- Proportion of participants with any escalation of treatment in the first 24 hours following IP initiation, i.e., any medication other than IP for the acute treatment of SE in the first 24 hours.
- Time to treatment escalation following IP initiation (any other medication used for acute treatment of SE).
- Time to initiation of anesthesia for SE treatment through the final study follow-up visit/contact.
- Proportion of participants who develop Super Refractory SE (SRSE) through the final study follow-up visit/contact.
- Seizure burden through 72 hours following IP initiation.
- Level of responsiveness as assessed by the Full Outline of UnResponsiveness (FOUR) Score Scale.
- Level of sedation/agitation as assessed by the Richmond Agitation and Sedation Scale (RASS).
- Clinician Global Impression-Improvement (CGI-I).
- Level of functioning as assessed by the modified Rankin Scale (mRS).

- Level of functioning as assessed by the EuroQoL (EQ-5D-5L).
- Proportion of participants with mRS ≥ 3 at the time of hospital discharge.
- Proportion of participants whose treatment does not progress to IV anesthesia for 4 weeks following IP initiation.

1.2.4 Healthcare Utilization Endpoints

The following healthcare utilization endpoints will be analyzed:

- Time on positive pressure ventilation after IP initiation.
- Proportion of participants requiring positive pressure ventilation initiated during IP infusion.
- Length of stay in intensive care unit (ICU) and in hospital after IP initiation.
- Discharge destination (location where the participant is residing at the last follow-up [FU] assessment).

1.2.5 Safety Endpoints

- Vital signs (height, weight, blood pressure [BP], pulse, respiratory rate [RR], body temperature, oxygen saturation).
- Electrocardiogram (ECGs).
- Clinical laboratory tests (hematology, chemistry and urinalysis, pregnancy and drug test).
- Physical exam findings.
- Use of concomitant medications.

Adverse events.

1.2.6 Open-label Phase Endpoints

If the study transitions to open label, all endpoint assessments as described for the double-blind phase will be summarized using descriptive statistics and no formal hypothesis testing will be performed.

1.2.7 Pharmacokinetic Endpoints

- Maximum plasma concentration (C_{max}).
- Time of maximum concentration (T_{max}).
- Area under the concentration versus time curve from time 0 to t hours (AUC_{0-t}).
- Area under the concentration versus time curve from time 0 to infinity (AUC_{inf}).

- Clearance (CL). Calculated as dose/AUC_{inf}.

1.3 Study Design and Flow Chart

[figure not shown]
1.3.1 General Study Design and Plan

This is a double-blind, randomized, placebo-controlled study to evaluate the efficacy and safety of ganaxolone IV solution in SE, with the option to transition the study to an open-label phase to obtain additional safety data. Open-label enrollment would commence if there were a finding of efficacy from the double-blind phase at the interim analysis. Approximately 160 patients 12 years and older with SE will be screened to randomize approximately 124 participants. Randomized participants will receive ganaxolone IV solution or placebo, referred to as investigational product (IP), in a 1:1 ratio added to standard of care treatment.

After the IP has been discontinued, participants will enter the follow-up period where assessments/procedures will be collected every 24 hours through 120 hours (or until hospital discharge) and at the time of hospital discharge, followed by weekly visits/contacts at Week 1, 2, 3, and 4 following IP initiation.

The Week 1, 2, 3, and 4 visits can be conducted as inpatient visits if the participant is still in the hospital, or as telephone visits if the participant has been discharged. Attempts should be made to have discharged participants return for one of these visits in person. Each participant will be followed for approximately 4 weeks following IP initiation ([Figure 1](#)).

Figure 1: Study Design Flow Chart

An interim analysis will be conducted when two-thirds of the ITT population have completed the co-primary and key secondary efficacy assessments. Based upon the interim analysis results, DMC review and recommendation and sponsor agreement, the double-blind phase may discontinue enrollment due to a determination of efficacy. Alternatively, the DMC will recommend continuing the study without modification or provide another recommendation. If the DMC recommends that the study has met the efficacy objectives at the interim analysis and the Sponsor agrees, the study will transition to open label. All subsequently enrolled participants will receive open-label ganaxolone IV solution added to SE standard of care.

If study enrollment is proceeding at a rate such that the study would be complete or nearly complete by the time an interim analysis is accomplished, the Sponsor may elect not to conduct it.

1.3.2 Sample Size and Power

The double-blind phase will randomize and treat approximately 124 participants. The sample size is based on the assumption of at least a 75% response rate to ganaxolone treatment for each of the co-primary endpoints and no more than 45% response rate to placebo treatment with a 1:1 randomization ratio.

With 62 evaluable participants in each treatment arm, there will be at least 90% power for each co-primary endpoint to achieve statistical significance at a 2-sided 5% level of significance.

After receiving the DMC recommendation that the study may continue after the interim analysis, the sponsor made the decision to stop enrollment of the study, at which point about 100 participants have been randomized.

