The time to SE cessation will be analyzed using the Kaplan-Meier method.²⁰ The comparison of the survival curves between treatment groups will be conducted by a log-rank test. The second key secondary endpoint will be analyzed using the same statistical model as pre-specified for the co-primary endpoints.

Further details will be provided in the SAP.

Data Monitoring Committee

Emerging study data will be reviewed on a regular basis by an independent Data Monitoring Committee (DMC). The mission of the DMC is to safeguard the interests of study participants and to ensure the integrity and credibility of the trial. To enable the DMC to achieve its mission, it will have ongoing access to efficacy and safety data and information regarding quality of trial conduct and will ensure that the confidentiality of these data is protected. A DMC charter will provide the principles and guidelines for the DMC process.

Sample Size

The planned sample size for the study was 124 participants randomized in a 1:1 ratio. This sample size assumed at least a 75% response rate with ganaxolone treatment for each of the co-primary endpoints and no more than a 45% response rate with placebo. With 62 participants randomized to each treatment arm, there would be at least 90% power for each co-primary endpoint to achieve statistical significance at a 2-sided 5% level of significance.

Interim Analysis

An interim analysis was planned when two-thirds of the ITT population have completed 72 hours of efficacy assessments on the co-primary and key secondary endpoints (approximately 41 participants per arm). The overall type I error rate (i.e., $\alpha=0.05$, 2-sided) will be controlled using a power family α spending function, with a 2-sided nominal α level of 0.0293 at the interim analysis. The interim analysis will be performed by an independent statistician who is not involved in study operation or study conduct.

The interim analysis was performed by an independent statistician who was not involved in study operation or study conduct and was based on 83 participants who had completed the primary and key secondary efficacy assessments. The DMC recommended may continue without modification.

Further details will be provided in the SAP.

STUDY SCHEDULE(S)

Table 1. Schedule of Assessments (Double-Blind and Open-Label Phases)

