3.1.1 Double-blind Phase

Approximately 160 participants were planned to be screened to randomize approximately 124 study participants at least 12 years of age with SE. Randomization stopped at 100 patients for business reasons. Randomized participants will receive ganaxolone IV solution or placebo, referred to as investigational product (IP), in a 1:1 ratio added to SE standard of care.

[figure not shown]
Potential participants may be identified in the emergency department, ICU or other units in the hospital and will be consented/assented or deferred, where allowed by law and then screened for inclusion/exclusion criteria prior to being randomized to start IP treatment.

Investigational product will be added to standard of care following failure of any two or more antiseizure treatments (benzodiazepine and 1 IV AED or 2 IV AEDs). Investigational product will be administered as a 48-hour continuous infusion, which includes an initial 3-minute bolus and ends with a 12-hour taper.

After the IP has been discontinued (with or without taper), the follow-up period study assessments/procedures will be collected every 24 hours through 120 hours (or until hospital discharge) and at the time of hospital discharge followed by weekly follow-up visits/contacts at Week 1, 2, 3, and 4.

Weeks 1, 2, 3, and 4 visits can be conducted as an inpatient visit for participants who are still in the hospital, or as a telephone contact for participants who have been discharged. Attempts should be made to have discharged participants return for one of these visits to be in person. In total, each participant will be followed for approximately 4 weeks following IP initiation.

Figure 1. Study Design Flow Chart

Treatment is planned to be 2-days (including a 12-hour taper).

Hours 24-36 should start with an infusion rate of 20mg/hr with dose adjustments allowed up to 45mg/hr.
Upon IP discontinuation (with or without taper) participant will continue into the Follow-up Period

Total participation is expected to be approximately 4 weeks.

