10.2 Sample Size Determination

Approximately 124 participants will be randomized and qualified for the study. The sample size is based on the assumption of at least 75% response rate to ganaxolone treatment for each of the co-primary endpoints and no more than 45% response rate to placebo treatment and 1:1 randomization ratio.

With 62 participants randomized to each treatment arm, there would be at least 90% power for each co-primary endpoint to achieve statistical significance at 2-sided 5% level of significance.

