10.4.1 Primary Endpoints (Double-Blind Phase)

The primary efficacy objective of this study is to assess the efficacy of ganaxolone plus standard of care versus placebo plus standard of care in producing rapid and durable SE cessation without the need for treatment escalation to IV anesthesia for at least 36 hours following IP initiation.

Since the primary efficacy objective is a composite objective, in order to establish effectiveness of ganaxolone and support approval, the superiority of ganaxolone vs placebo added to standard of care would need to be established for the following co-primary endpoints:

1. Proportion of participants with SE cessation within 30 minutes of IP initiation without medications for the acute treatment of SE
2. Proportion of participants with no progression to IV anesthesia for 36 hours following IP initiation

SE cessation will be determined by the investigator based on clinical and EEG features (see Appendix 1 for SE cessation guide). Training will be provided to guide and help standardize decisions across clinical sites. In addition, a retrospective, confirmatory analysis of time of SE cessation will be performed by a central EEG reader blinded to treatment assignment.

Medications for the acute treatment of SE are defined as AEDs administered to abort ongoing SE or prevent imminent recurrence of SE based on clinical or EEG evidence. This definition excludes maintenance doses of AEDs or medications with anticonvulsant properties used for other reasons, such as procedural sedation.

Both co-primary efficacy endpoints must be statistically significant to claim the study being positive. No ordering is involved in the hypothesis testing of the two co-primary endpoints.

The efficacy analysis of the response rates observed for each co-primary endpoint will be conducted by using logistic regression methods. The model will include terms for treatment group and baseline STESS as a covariate. The analysis will be based on the ITT population. Model-based point estimates (i.e., odds ratio), 95% confidence intervals and p-values will be reported. In addition, the point estimate of difference of the proportions of participants achieving either and both co-primary endpoints between two treatment arms will be provided. The 95% confidence interval will be provided using Clopper-Pearson method.⁴¹

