10.7 Interim Analyses

An interim analysis was planned when two-thirds of the ITT population have completed 72 hours of efficacy assessments on the co-primary and key secondary endpoints (approximately 41 participants per arm). The overall type I error rate (i.e., $\alpha=0.05$, 2-sided) will be controlled using a power family α spending function, with a 2-sided nominal α level of 0.0293 at the interim analysis. The interim analysis will be performed by an independent statistician who is not involved in study operation or study conduct.

The interim analysis was performed by an independent statistician who was not involved in study operation or study conduct and was based on 83 participants who had completed the primary and key secondary efficacy assessments. The DMC recommended that the study may continue without modification.

To control the overall type I error rate (i.e., a two-sided α level of 0.05), the α value for the final analysis will be adjusted by the final sample size. For example, if the final analysis sample size is 100, the two-sided α level for the final analysis is 0.0410.

Further details will be provided in the SAP.

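### Protocol 10.7 and the SAP prescribe different final tests (0.0410 versus a combination test at 0.0343), and neither gives power for the 83 + 17 participants to be analysed

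*SAP*

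**What the plan says.** **Sample size and power.** SAP 1.3.2 opens with "The double-blind phase will randomize and treat approximately 124 participants" and gives the power as "With 62 evaluable participants in each treatment arm, there will be at least 90% power for each co-primary endpoint to achieve statistical significance", at two-sided 5% and response rates of 75% versus 45%. The same section then reports that the sponsor stopped enrolment, "at which point about 100 participants have been randomized". Protocol 10.2 gives the same figure: "there would be at least 90% power for each co-primary endpoint to achieve statistical significance at 2-sided 5% level of significance". The protocol synopsis (Sample Size) uses the past tense, "The planned sample size for the study was 124 participants randomized in a 1:1 ratio", and protocol 3.1.1 says "Randomization stopped at 100 patients for business reasons". Neither document gives power for about 100 participants.

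**Decision rule.** Protocol 10.4.1: "Both co-primary efficacy endpoints must be statistically significant to claim the study being positive". Under SAP 3.5, if either co-primary misses at the interim, both are tested again at the final analysis.

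**Final test.** Protocol 10.7, in text that already reports the 83-participant interim, says that the alpha "value for the final analysis will be adjusted by the final sample size" and gives 0.0410 at 100 as an example. Protocol 10.4.1 names logistic regression on treatment and baseline STESS. SAP 3.2.1.1 and 3.5 use a fixed-weight combination of the interim logistic p-value and a Boschloo p-value from the later participants, at the 0.0343 calculated for the original plan. Earlier in SAP 3.5 a parenthesis allows 0.0343 to be adjusted. SAP section 4 declares no change from the protocol. The SAP version 4.0 log records an updated testing procedure requested by FDA.

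**The concern.** Two current documents give different critical values and different test statistics for the confirmatory analysis, and the section meant to list departures lists none. The record should show, before anyone sees the final data, which test decides the trial.

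The power statement matters for interpretation. A non-significant result would be read against a figure of at least 90% that belongs to a trial of 124 tested once at 5%. The trial to be analysed has about 100 participants, two looks, a combination test and a requirement that both co-primaries succeed.

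**Working it through.** **1. The plan's own power.** Inputs from SAP 1.3.2: 0.75, 0.45, n = 62 per arm, alpha 0.05.

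Power = Φ{[0.30√62 − 1.96√(2 × 0.60 × 0.40)] / √(0.75 × 0.25 + 0.45 × 0.55)} = Φ{(2.362 − 1.358)/0.660} = Φ(1.52) = 93.6%.

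The stated figure of at least 90% is reproduced. At alpha 0.0343 the same formula gives 91.3%.

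**2. The two alphas.** The spending function is 0.05·t^(log 2.5/log 2), exponent 1.322. At t = 2/3 it spends 0.02925 (stated 0.0293). The final alpha solves P(|Z1| < c1, |Z| < c2) = 0.95 with correlation √t.
- t = 2/3: 0.0343, the SAP's value (c2 = 2.117)
- t = 83/100 with 0.0293 spent: 0.0410, the protocol's value

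Both are correct, each for its own procedure.

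**3. Power per co-primary under the SAP test.** Z = √(2/3)·Z1 + √(1/3)·Z2. Stage 1 is 83 participants (42/41 or 41/42). Stage 2 is 100 − 83 = 17 (8/9 or 9/8). Critical values are 2.179 at the interim and 2.117 at the final. Stage 1 uses an unadjusted score or Wald test in place of the logistic model; stage 2 uses the one-sided Boschloo test. Exact binomial enumeration at 75% versus 45% gives:

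| Quantity | Probability |
|---|---|
| Significant at the interim (I) | 72.6–73.8% |
| Significant at the final look (F) | 79.6–81.2% |
| Significant at either look (E) | 84.4–85.4% |

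Normal check for F: mean Z1 = 0.30/√(0.48/41.5) = 2.790; mean Z2 = 0.30/√(0.48/8.5) = 1.262; combined 0.8165 × 2.790 + 0.5774 × 1.262 = 3.007; SD √(0.435/0.48) = 0.952. Φ{(3.007 − 2.117)/0.952} = 82.5%. The enumeration is a little lower.

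**4. Both co-primaries.** Success means both at the interim or both at the final. If the endpoints are independent, power is I² + F² − (I + F − E)².
- Lowest case: 0.7259² + 0.7960² − 0.6777² = 0.701
- Highest case: 0.7384² + 0.8118² − 0.6962² = 0.720
- Fully correlated endpoints: E, or 84.4–85.4%

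On the same basis the original two-look plan (82, then 42) gives 92% per endpoint and 85% for both if independent.

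**5. Disagreement between the two tests.** The protocol is read here as one unadjusted test on all 100 at 0.0410. On the same simulated data, per endpoint:
- the protocol's test alone is significant in 4.9–5.8% of trials
- the SAP's test alone is significant in at most 0.6%
- total disagreement is 5.4–6.4%

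With the score test, 2.2–2.6 points of this fall where the endpoint missed at the interim. Given such a miss, that is 2.2/26.2 to 2.6/26.3, about 8–10%.

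**6. Power difference between the two tests.** The protocol's version gives 84.7–86.4% at the final look and 85.8–87.3% at either look. Against step 3, the SAP test costs about 5 points at the final look alone and 1–2 points at either look.

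**The case against.** **Which test governs.** Protocol 10.1 and 10.7 defer detail to the SAP, 0.0410 is offered only as an example, and the SAP log records that the procedure was updated at FDA's request. SAP 3.2.1.1 and 3.5 agree with each other. This largely stands: the intended test is the combination test at 0.0343. A reader might infer that the sponsor is free to choose a test after unblinding, and the documents do not support that. What remains is that protocol 10.7 describes a different rule and SAP section 4 denies any difference, which the log contradicts.

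**The adjustment parenthesis.** It belongs to the general plan, and the next paragraph of SAP 3.5 says what is done after the stop. That stands, so only a clarifying sentence is needed.

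**Power after enrolment has closed.** A new figure changes neither the data nor the threshold, and the planned odds ratios and confidence intervals say more about precision. The calculation also needs inputs that the documents omit. This is fair and limits the weight of the power point. But the SAP section was revised to report the stop and the old power was left beside it, so the record should say which trial that figure describes.

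**The disagreement rate.** A reader might take 5–6% as the chance that the trial's verdict flips. It is not. It is per endpoint and unconditional, and more than half of it concerns endpoints already significant at the interim, where it matters only if the other co-primary missed. The documents do not report the interim results.

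**Conclusion.** The protocol and SAP conflict on the final test and alpha, and SAP section 4 fails to record it. At the design rates the two tests give different answers on a given endpoint in about 5–6% of trials, including 2.2–2.6 points where that endpoint missed at the interim.

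The stated power is out of date, not miscalculated. A reader might call the 90% an arithmetic error, but it is correct for the original plan and the stop at 100 is disclosed. For the 83 + 17 to be analysed it is about 80–81% per co-primary at the final look and 84–85% at either look. For both co-primaries it is 70–72% if independent, rising to 84–85% if fully correlated.

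Nor does the mismatch show that the SAP test inflates type I error. With a common rate of 45%, enumeration of one split (41/42, then 9/8) gives a one-sided either-look error of 0.022–0.023 per endpoint, below 0.025.

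These figures assume 75% versus 45%, near-equal arms, all 100 in ITT, no missing data and no STESS effect. Fewer ITT participants after the interim would lower them. The documents give no STESS effect. Assuming 0.5 or 1.0 log-odds per SD, simulated power is 81–82% or 84–85% at the final look and 86–87% or 89–90% at either look; the 124-participant plan rises too, to 94% or 96%. An unpooled normal approximation gives 85% and 88% with no STESS effect. The correlation between the co-primaries is not given, hence the joint range.

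**What to change.** Before unblinding:

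1. Amend protocol 10.7 to name the SAP's fixed-weight combination test at two-sided 0.0343, and remove the sample-size adjustment and the 0.0410 example.
2. Replace the statement in SAP section 4 with an entry recording the change of test and alpha and the reason given in the version log.
3. State in SAP 3.5 that the adjustment allowed for 0.0343 was not exercised.
4. Label 124 participants and at least 90% power as the original plan in SAP 1.3.2 and protocol 10.2.
5. Add to SAP 1.3.2 the power for about 100 participants under the combination test: per co-primary at the final look and at either look, and for both together. Give the assumptions on response rates, ITT count, STESS effect and correlation. Note that a single co-primary winning at the interim is not a decision, because both are retested.

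The cost is a few paragraphs of text and a less favourable stated power. The SAP's own test and threshold stay as they are. Confirming that test gives up about 1–2 points of either-look power per co-primary against the protocol's version, or about 5 points at the final look alone.
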